18.1.1. All TEAEs

All TEAEs will be summarized by SOC and PT and presented by descending frequency in the etrasimod group. All AEs, regardless of treatment-emergent status, will be included in an AE listing. Additionally, a listing of other AE details as collected on the CRF will be presented.

Exposure-adjusted incidence rate (EAIR) of TEAEs will be summarized by SOC and PT. Exposure is defined as the sum of either time (year) from first dose in Study APD334-308 to the onset of first such event for those who experienced this AE in Study APD334-308, or time (year) from first dose in Study APD334-308 to last participation for those who did not experience this AE. The EAIR is calculated as the number of subjects with the AE divided by the total exposure in subject-years.

18.1.1.1. Severity

Severity is classified as Grade 1: Mild, Grade 2: Moderate, Grade 3: Severe, Grade 4: Life Threatening, Grade 5: Death Related to AE, using the Common Terminology Criteria for Adverse Events, version 5.0 (CTCAE v5.0).

All TEAEs will be summarized by SOC, PT, and maximum severity, with SOC and PT presented by descending frequency. If a subject reports a TEAE more than once within a SOC/PT, the AE with the worst-case severity will be used in this summary.

18.1.1.2. Relationship to Study Treatment

Relationship is classified as “not related”, “unlikely related”, “probably related”, or “related” by the Investigator.

All related TEAEs will be summarized by SOC and PT. A “related TEAE” for the purpose of this summary is defined as a TEAE with relationship to study drug of “probably related” or

“related”.

All TEAEs will be summarized by SOC, PT, and highest relationship (as reported on the eCRF, not grouped), with SOC and PT presented by descending frequency. If a subject reports a TEAE more than once within a SOC/PT, the AE with the worst-case relationship to study treatment will be used in this summary. TEAEs with a missing relationship to study treatment will be regarded as “Related” to study treatment for summary tabulation purpose only.

18.1.2. TEAEs Leading to Discontinuation of Study Treatment

TEAEs leading to discontinuation of study treatment will be identified by action taken being recorded as “Drug withdrawal” on the Adverse events eCRF.

All TEAEs leading to discontinuation of study treatment will be summarized by SOC and PT. A listing of all TEAEs leading to discontinuation of study treatment will also be presented.

Liver-related AEs are defined by either SOC of hepatobiliary disorders or PT of alanine aminotransferase abnormal, alanine aminotransferase increased, aspartate aminotransferase abnormal, aspartate aminotransferase increased, hepatic enzyme abnormal, hepatic enzyme increased, liver function test abnormal, liver function test increased, transaminases abnormal, or transaminases increased.

18.1.3. Serious and Non-Serious TEAEs

Serious adverse events (SAEs) are those events recorded as “Serious” on the Adverse Events page of the eCRF. A summary of serious TEAEs by SOC and PT will be prepared.

All serious TEAEs will be summarized by SOC and PT. If the seriousness is missing, the AE will be considered as “Serious” for the summary tabulation purpose only. A serious TEAE listing will also be presented. All non-serious TEAEs will also be summarized by SOC and PT.

18.1.4. TEAEs Leading to Death

TEAEs leading to Death are those events which are recorded with an outcome as “Fatal” on the Adverse Events eCRF. A listing of TEAEs leading to death will be presented.

18.1.5. TEAEs of Special Interest

Categories of Targeted Medical Events (TMEs) and a list of preferred terms associated with these TME categories were developed based on the mechanism of action of etrasimod, prior experience with other agents acting via a similar mechanism, and disease-specific clinical judgment. In addition, where standard testing has been implemented to screen for potential AESI (eg, electrocardiograms, spirometry, serum transaminases, etc.), the relevant data will be reviewed to identify potential cases of AESI that investigators may not have identified and to provide quantitative data for AESIs. The proposed candidate terms will be reviewed to identify which events reflect AESI.

Treatment-emergent AESIs will be summarized by category, subcategory, and PT by descending frequency by treatment group. Categories and subcategories of TEAEs of special interest are the

following:

- Cardiovascular Events
 - Bradycardia
 - AV conduction delay
 - Hypertension
- Macular Edema
- Pulmonary Disorders
 - Airflow obstruction (forced expiratory volume in 1 second [FEV1], forced vital capacity [FVC])
 - Decrease gas exchange (diffusing capacity of the lungs for carbon monoxide [DLCO])
- Infections
 - Severe infections
 - Opportunistic infections (Narrow)
 - Herpes simplex and herpes zoster
- Liver Injury
 - Liver transaminases elevation
 - Bilirubin elevation
- Posterior Reversible Encephalopathy Syndrome (PRES)
- Malignancies

Exposure-adjusted incidence rate of AESI by category, by subcategory and by PT with 95% CI, and rate difference from placebo and 95% CI will be reported in an integrated analysis combining APD334-302 and APD334-308 data.

18.1.6. Overall Summary of Adverse Events

In addition to the summaries above, an overview of TEAEs will be summarized (not broken down by SOC or PT) by number and percentage of subjects and by number of AEs:

- Any TEAEs
- Any related TEAEs
- Any serious TEAEs
- Any related serious TEAEs
- TEAEs leading to death

- Liver-related TEAEs leading to death
- TEAEs leading to study drug discontinuation
 - Related TEAEs leading to study drug discontinuation
 - Liver-related TEAEs leading to study drug discontinuation
- TEAEs leading to study drug interruption
 - Related TEAEs leading to study drug interruption
- TEAEs by maximum severity
 - Related TEAEs by maximum severity
- TEAEs by relationship to study drug

*Related TEAEs' refers to TEAEs related or probably related to study drug.

Comparative analyses will be performed for:

- Deaths
- Serious TEAEs
- TEAEs leading to study treatment discontinuation
- TEAEs of special interest
- Serious infections
- Opportunistic infections (Narrow)
- Malignancies

18.2. Deaths

Information collected about deaths (e.g., date of death, primary cause of death) will be presented in a data listing, as described in Section 18.1.4.

18.3. Laboratory Evaluations

No local laboratory assessments will be used in any summaries except for lipid panel and thyroid panel tests. No local laboratory assessments will be used to derive maximum/minimum/worst value. Local laboratory assessments will only be listed.

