9.8.7. Clinical Laboratory Tests

Refer to Table 6 for the list of clinical laboratory tests to be performed and the Schedule of Assessments (Table 7) for timing and frequency for each test. Details regarding clinical laboratory sample collection, preparation, and shipment are provided in the Laboratory Manual by the central laboratory.

Clinical safety laboratory tests should be completed predose. The Investigator must review the laboratory report, document this review, and record any clinically relevant changes occurring during the study in the adverse event section of the eCRF (results of the total WBC and ALC will be reviewed and monitored as described in Section 9.7.4). The laboratory reports must be filed with the source documents. Clinically significant abnormal laboratory findings are those that are not associated with the underlying disease, unless judged by the Investigator to be more severe than expected for the subject's condition.

All laboratory tests with values considered clinically significantly abnormal during participation in the study or within 30 days after the last dose of study treatment should be repeated until the

values return to normal or baseline or are no longer considered clinically significant by the Investigator or Medical Monitor.

- If such values do not return to normal/baseline within a period of time judged reasonable by the Investigator, the etiology should be identified, and the Sponsor should be notified.
- All protocol-required laboratory assessments, as defined in the Schedule of Assessments (Table 7) must be conducted in accordance with the Laboratory Manual.
- If laboratory values from non-protocol-specified laboratory assessments performed at the institution's local laboratory require a change in subject management or are considered clinically significant by the Investigator (eg, adverse event, SAE, or dose modification), then the results must be recorded in the eCRF.

For guidance on monitoring subjects with notable lymphopenia, please refer to Section 9.7.4.

Table 6: Clinical Laboratory Tests

PREGNANCY TESTING Urine β-hCG (only for women of c	hildbearing potential)			
CLINICAL CHEMISTRY, HEMATOLOGY, AND COAGULATION				
Hematology	Serum Chemistry			
CD4 T-cell count ^a	Alanine aminotransferase	Potassium		
Hematocrit	Albumin	Sodium		
Hemoglobin	Alkaline phosphatase	Thyroid-stimulating hormone		
Mean corpuscular hemoglobin	Aspartate aminotransferase	Thyroxine free		

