6.3. Retests, Unscheduled Visits and Early Termination Data

For by-visit analyses and summaries, efficacy, safety, HRQoL, and biomarkers data (including scheduled, retests, unscheduled, and early termination) will be assigned to visits after the application of the windowing conventions described in Section 6.4. All measurements will be considered in summaries of abnormalities or worst-case values post Baseline.

Listings will include scheduled, unscheduled, retest, and early termination data.

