18.3.1. SAFETY LABORATORY EVALUATIONS

Hematology, serum chemistry, coagulation, and urinalysis are analyzed and reported by central laboratory and sometimes by local laboratory. Results out of reference range are flagged by the performing laboratory (e.g., low, high). A full list of laboratory assessments to be included in the outputs is included in Clinical Study Protocol APD334-308 Table 7.

In general, presentations will use SI Units. Quantitative laboratory measurements reported as “ $< X$ ” or “ $> X$ ”, where X may be the lower limit of quantification (LLQ) or the upper limit of quantification (ULQ), respectively, will be converted to X for the purpose of quantitative summaries, but will be presented as recorded, i.e. as “ $< X$ ” or “ $> X$ ” in the listings. For urinalysis, only pH and specific gravity are considered as quantitative tests. If local and central laboratory assessments are available from the same day, central laboratory assessments will be used in the summary as per Section 18.3.1.

The following summaries will be provided for laboratory data:

- Value and change from Baseline by visit (for hematology, serum chemistry, quantitative urinalysis [pH and specific gravity], and coagulation)
- Incidence of abnormal values according to laboratory reference ranges by visit
- Incidence of lymphocytes $< 0.2 \times 10^9/L$, $0.5 \times 10^9/L$, or neutrophils $< 0.5 \times 10^9/L$, $1 \times 10^9/L$ at Week 52 and anytime after first dose in Study APD334-308
- Shift from end of treatment to each followup visit in incidence of lymphocytes in normal range and in incidence of lymphocytes of at least 80% percent of Baseline, by visit (2-Week Follow-Up, 4-Week Follow-Up, and Last FollowUp)Shift from Baseline to Week 52/Early Termination Visit according to laboratory reference range (for quantitative measurements and categorical measurements)
- Evaluation of Drug-Induced Serious Hepatotoxicity (eDISH) plots for the following laboratory assessments (using values after the first administration of study treatment):
 - Maximum aspartate aminotransferase (AST) versus same-day total bilirubin
 - Maximum alanine aminotransferase (ALT) versus same-day total bilirubin
 - Maximum gamma-glutamyl transferase (GGT) versus same-day total bilirubin
 - Maximum alkaline phosphatase (ALP) versus same-day total bilirubin

The eDISH plots above will be repeated with adjustment for elevated Baseline.

- Incidence of hepatic enzyme elevations by visit

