 - $> 1 \times$, $2 \times$, $3 \times$, $5 \times$, $8 \times$, $10 \times$, $20 \times$ upper limit of normal (ULN) elevation in ALT
 - $> 1 \times$, $2 \times$, $3 \times$, $5 \times$, $8 \times$, $10 \times$, $20 \times$ ULN elevation in AST
 - $> 3 \times$, $5 \times$, $10 \times$, $20 \times$ ULN elevation in either ALT or AST
 - $> 1 \times$, $1.5 \times$, $2 \times$, $3 \times$ ULN elevation in total bilirubin
 - $> 1 \times$, $1.5 \times$, $2 \times$, $3 \times$, $5 \times$, $8 \times$ ULN elevation in ALP
 - $> 1 \times$, $2 \times$, $3 \times$, $5 \times$, $8 \times$ ULN elevation in GGT
 - $> 3 \times$ ULN elevation in either ALT or AST and $> 1.5 \times$ ULN elevation in total bilirubin
 - $> 3 \times$ ULN elevation in either ALT or AST and $> 2 \times$ ULN elevation in total

bilirubin

- $> 3 \times$ ULN elevation in either ALT or AST and $> 1.5 \times$ ULN elevation in ALP
- $> 3 \times$ ULN elevation in either ALT or AST in temporal association with treatment-emergent nausea, vomiting, anorexia, abdominal pain, or fatigue identified by PT, where temporal association is defined as ± 14 days of onset date from the time of elevation.

If both central and local assessments of total bilirubin are available on the same day, the central result will take precedence over the local result in the eDISH plot. If the maximum AST/ALT/GGT assessment occurs at two 2 different dates, the assessment with the higher accompanying Bilirubin value will be used. Two versions of the eDISH plots will be presented, with one showing values as multiples of upper limit of normal, and the other one showing values as multiples of upper limit of normal, or subject's baseline, whichever is higher. Subject's laboratory assessments at all timepoints will be listed in chronological order. Values outside of the laboratory reference range will be flagged. Values obtained from local laboratory will be flagged. Listing of lymphocytes and neutrophils over time in subjects ever with lymphocytes $< 0.5 \times 10^9/L$ or neutrophils $< 1 \times 10^9/L$ will also be provided.

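### The SAP's rules on local laboratory results conflict, and its eDISH plots and combined liver rows can omit a joint ALT/AST and bilirubin elevation on different or off-schedule days

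*SAP*

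**What the plan says.** **Local results.** SAP Section 18.3 has three sentences on them. The first is "No local laboratory assessments will be used in any summaries except for lipid panel and thyroid panel tests". The second is "No local laboratory assessments will be used to derive maximum/minimum/worst value". The third is "Local laboratory assessments will only be listed", which does not fit the exception in the first.

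Three other places treat local results as usable:
- SAP Section 6.3: "All measurements will be considered in summaries of abnormalities or worst-case values post Baseline". It makes no exception for local values.
- SAP Section 6.4 gives the central value precedence over the local one for the same laboratory test or ECG, but only when both fall on the same day.
- SAP Section 18.3.1 repeats this for laboratory summaries ("If local and central laboratory assessments are available from the same day, central laboratory assessments will be used in the summary") and for total bilirubin: "the central result will take precedence over the local result in the eDISH plot".

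**Liver displays.** Section 18.3.1 plans eDISH plots for AST, ALT, GGT and ALP, each of the form "Maximum alanine aminotransferase (ALT) versus same-day total bilirubin". If an AST, ALT or GGT maximum occurs on two dates, the date with the higher bilirubin is used. A separate table gives hepatic elevations by visit. It includes rows for ALT or AST above 3 x ULN together with bilirubin above 1.5 x or 2 x ULN.

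**Protocol.** Section 9.1 makes the central laboratory the default for protocol-required tests. Section 9.8.7 requires results of non-protocol local tests in the eCRF when they "require a change in subject management or are considered clinically significant by the Investigator". The liver criterion in Section 5.1 combines ALT or AST above 3 x ULN with bilirubin above 2 x ULN (or INR above 1.5) and sets no same-day condition.

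**The concern.** Two programmers could each follow the SAP faithfully and produce different liver outputs, depending on whether they start from Section 18.3 or from Sections 6.3 and 6.4.

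The local values at issue are not a random subset. Those that Protocol Section 9.8.7 sends to the eCRF were judged clinically significant or changed how the subject was managed. Scheduled laboratory visits are 8 weeks apart from Week 24 to Week 48 (Protocol Table 7), so an acute event between visits may have a local result and no central one near it.

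The second issue arises even if every sample is central. Bilirubin may peak on a different day from the enzyme. A plot tied to the day of the enzyme maximum, and a row tied to one value per visit, can then both fail to show a subject whose results meet the joint criterion. At stake is the numerical liver display in a study of about 35 subjects, where a single joint elevation would matter to the liver conclusion.

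**Working it through.** The plan states no figure here, so the check sets its rules side by side and applies them to invented values. The windows and rules come from the SAP.

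**Step 1. Does a local bilirubin or transaminase count when no central result exists that day?**

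| SAP section | Implied answer |
|---|---|
| 18.3 | No: listing only |
| 6.3 | Yes: all measurements enter abnormality and worst-case summaries |
| 6.4 | Yes by implication: central wins only when both exist that day |
| 18.3.1, summaries | Yes by implication, but could serve only the lipid and thyroid exception |
| 18.3.1, eDISH bilirubin | Yes by implication; bilirubin is neither a lipid nor a thyroid test |

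The bilirubin sentence cannot be rescued by the exception. A rule ranking central over local bilirubin in the plot has no use if local bilirubin can never be plotted. Sections 6.3 and 6.4 are general and carry no exclusion.

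**Step 2. Effect of the local-data conflict alone.** Assume a central sample on Day 170 with ALT 4 x ULN and bilirubin 1.2 x ULN, and a local sample on Day 178 with ALT 6 x ULN and bilirubin 2.5 x ULN.
- Under Section 18.3 the plotted point is (4, 1.2).
- Under Sections 6.3, 6.4 and the eDISH sentence it is (6, 2.5).

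The second point lies beyond 3 x ULN for ALT and 2 x ULN for bilirubin. The first does not.

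**Step 3. Effect of the pairing rules alone.** Assume all samples are central: Day 170 with ALT 6 x ULN and bilirubin 1.2 x ULN, Day 178 with ALT 4 x ULN and bilirubin 2.5 x ULN.
- *eDISH plot.* The ALT maximum is on Day 170, so the point is (6, 1.2), below 2 x ULN for bilirubin. The tie rule does not apply because the maximum occurs once.
- *Combined row by visit.* Both days lie in the Week 24 window for safety laboratory data (Days 156 to 197). The scheduled day is 169. The distances are |170 - 169| = 1 and |178 - 169| = 9, so Section 6.4 selects Day 170. Bilirubin 1.2 does not exceed 2, and the row is not met.
- *All measurements.* Day 178 alone meets the criterion (4 > 3 and 2.5 > 2). Maximum against maximum gives (6, 2.5).

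If Section 6.3 is taken to override Section 6.4 for this table, Day 178 counts. The SAP does not say which governs. Section 6.3 sets no pairing window either, so an ALT in one visit window and a bilirubin in the next have no stated treatment.

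**Step 4. Would admitting local values be enough?** No. In Step 2 the nearest-day rule still selects Day 170 for the combined row, so that row stays unmet even with local results allowed. The two issues need separate changes.

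**Gaps noticed in passing.** There is no rule for an enzyme maximum without a same-day bilirubin, and the tie rule omits ALP.

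**The case against.** Several points on the other side have force.

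- **Central-only is a legitimate choice.** It avoids mixing assays and reference ranges. This stands, but the SAP must then withdraw the sentences that assume otherwise.
- **The precedence rule for summaries in Section 18.3.1 need not contradict Section 18.3.** Cholesterol, triglycerides and thyroid tests are in the chemistry panel (Protocol Table 6), so the rule could serve that exception. This stands. The conflict rests on Section 6.3, Section 6.4 and the eDISH bilirubin sentence.
- **Same-day pairing is defensible.** A maximum-against-maximum plot can join values that never coexisted. This stands, and is why the existing plots should be kept.
- **Few values should be affected.** Protocol tests are central by default. This stands.

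A reader might infer more than the documents support:

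- *That every liver output pairs only on the same day.* Only the eDISH plots do. The table gives bilirubin elevations separately, and its combined rows state no same-day condition.
- *That a case could vanish from every summary.* Clinically relevant changes go to the adverse event page (Protocol Section 9.8.7). SAP Section 18.1.5 tabulates liver injury and has test data reviewed for cases that investigators may not have identified. Section 18.1.6 tabulates liver-related events leading to discontinuation. All results are listed, with local ones flagged.
- *That lymphocyte and neutrophil displays lose their lowest values.* Investigators are blinded to these counts and an unblinded monitor reviews them (Protocol Table 6 footnote). Nothing shows that on-treatment local counts would exist.

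**Conclusion.** The point holds in two limited parts. First, the SAP is contradictory on whether a local bilirubin or transaminase counts when there is no central result that day. Second, a joint elevation on different or off-schedule days can be missing from the eDISH plots and the combined rows, the latter if the nearest-day rule governs them. What is lost is visibility in plots and numerical rows. The data themselves stay in the listings, and clinically significant cases in the adverse event tables.

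The effect cannot be sized, because the documents do not say how many local results exist or how often peaks fall on different days. For scale only: 35 planned subjects at 2:1 give 35 x 2/3 = 23 on etrasimod, so one subject is 1/23 = 4.3 percentage points. Allocation was not controlled within Japan; for an assumed 20 to 26 subjects the figure is 1/20 = 5.0 to 1/26 = 3.8 points. That is true of any single event and is not evidence that one would be missed.

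The examples use invented values and show only that the rules can give different answers. The text needs correcting whichever local-data policy is preferred.

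**What to change.** 1. State one rule for local results and use it in SAP Sections 6.3, 6.4, 18.3 and 18.3.1. Either keep central-only as primary and add a supportive hepatic worst-value and eDISH output that uses local values (as multiples of the local laboratory's ULN) when no central result exists that day, or do the reverse. Reword the listing-only sentence in Section 18.3 to fit the lipid and thyroid exception.
2. Keep the same-day eDISH plots. Add one of maximum ALT/AST against maximum total bilirubin after first dose.
3. Add an any-time post-dose row for ALT or AST above 3 x ULN with bilirubin above 2 x ULN, using all measurements and stating any pairing window. Say whether Section 6.3 or the nearest-day rule in Section 6.4 governs the by-visit rows.
4. While editing, say what happens when an enzyme maximum has no same-day bilirubin, and extend the tie rule to ALP.

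The cost is SAP wording and modest programming. Local reference ranges must be in the database, and assay variation has to be accepted in whichever output uses local values. Points in the maximum-against-maximum plot may join different dates, so each one in the joint-elevation area needs a review of timing.
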